## METHODS

### B. Participant selection

**Participants:** A total of 240 women ages 45-65 who have been diagnosed with stage I-IIIA breast cancer will be recruited 1-8 years after the completion of all primary cancer treatment except for longer-term hormonal therapies (tamoxifen, aromatase inhibitors). We will recruit women who have received one of the two most common stage I-IIIA chemotherapy regimens, either docetaxel/cyclophosphamide or doxorubicin/cyclophosphamide followed by paclitaxel to provide uniformity of prior treatment. All women will be postmenopausal, defined as having FSH and estradiol within the institutional postmenopausal range at the time of study entry and no menstrual cycle in the last 12 months.

Cardiorespiratory fitness is a key variable, and it is thus important to select women who represent the full range of fitness. We anticipate that recruiting women at the lower end of fitness will not be a problem, but may represent a greater challenge in recruiting the most fit women. We will screen women prior to any in-person appointments using the CHAMPS [152-155] to maximize selection of more active women, particularly at higher BMIs. Although central adiposity will be inversely associated with  $VO_{2\text{peak}}$ , we will make sure to carefully select women who have lower central adiposity but are less fit, as well as women with higher central adiposity who have higher levels of activity and are more fit [156-159].

Most women who had estrogen receptor positive breast cancer will be on aromatase inhibitors or tamoxifen. We will collect information about these medications. Some evidence suggests that aromatase inhibitors and tamoxifen may affect cardiovascular risk [160, 161], while other studies did not observe a difference in risk [162] suggesting that this link requires further research at this time [163]. To our knowledge, the effect of these medications on acute cardiovascular changes has not been tested. Accordingly, we will include aromatase inhibitor and tamoxifen use as covariates in secondary analyses to assess whether these medications impact cardiovascular and inflammatory outcomes.

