Diagnostic, treatment, and staging data will be obtained from medical records. These data will include (but are not limited to): types and dates of diagnostic procedures, histology, cytology, tumor grade, available genetic tests, comorbidities, major medications, and hormonal treatment status. Where possible we will use the James Cancer Registry and Outcomes Management Department and/or the OSU Information Warehouse to provide us with information regarding our participants' treatment.

**Online/phone screening:** To confirm eligibility, we will collect data on cancer stage, time since treatment, and treatment regimen. We will also assess vaccination history, medication use, comorbidities, and physical activity.

**Screening session:** When subjects come for their in-person screening appointment at the Clinical Research Center (CRC), a hospital research unit, nurses will draw blood for assessment of anemia and hemoglobin A1C (to confirm  $< 6.5$ ). The nurses will also assess any potential phlebotomy problems, and measure blood pressure, height, and weight. Women will be interviewed using the mood and anxiety disorder modules from the Structured Clinical Interview for DSM-V [171, 172], nonpatient version.

**Cardiorespiratory fitness:** Peak oxygen consumption ( $VO_2\text{peak}$ ) will be evaluated at a screening visit using a graded cycle ergometry exercise test, starting at 25 watts and increasing by 25 watts every two minutes, with continuous monitoring via 12-lead EKG (MedGraphics Cardio2, Cardio Perfect).  $VO_2\text{peak}$  [173] will be calculated from 10-second averages of breath-by-breath expired air (MedGraphics Cardio2, Breeze Suite). Declines in cardiorespiratory fitness may result directly from chemotherapy's toxic effects on pulmonary, cardiac, hematological, vascular, and skeletal muscle function, as well as deconditioning following treatment [174]. Cardiorespiratory endurance is the gold standard measure of physical fitness; low values predict mortality [175-177]. To avoid influencing vaccine/placebo responses, this session will not occur on the day before a full-day CRC visit.

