## **E. Specimen Collection**

**Assays and Timing of Blood and Saliva Samples: Fasting levels of glucose and insulin** will be assessed prior to breakfast. HOMA-IR [291] will be used as a covariate in our analyses as an estimate of insulin resistance. The assays will be conducted by the hospital labs using standard methods. Insulin resistance will be assessed, based on data that suggests that higher proinflammatory cytokine responses to stress occurred among individuals with greater insulin resistance [292].

Typhoid vaccine provokes a transient acute phase response, with increases in proinflammatory cytokines followed by rises in anti-inflammatory cytokines [48-60]. To assess the magnitude and duration of these changes, blood will be drawn for **IL-6, TNF- $\alpha$ , IL-10, IL-1Ra, sTNF-RII, and SAA** in serum samples measured using an electrochemiluminescence method with Meso Scale Discovery kits at the fasting baseline and then every 90 minutes post-inoculation for 7.5 hours. The choice of assays was based on changes observed following typhoid inoculation and related endotoxin studies, and was designed to provide data on kinetics of both pro- and anti-inflammatory markers [48-60]. Our laboratory has had many years of experience in measuring proinflammatory cytokines [142, 143, 146, 147, 165]. The stored serum samples for each subject will be assayed for all the cytokine markers in one run, thus using the same controls for all time points for each person. High-sensitivity **CRP assays** will be performed by the hospital lab using standard procedures. Across both full-day admissions we will have a total of 12 **CBCs with differential**, coinciding the timing with the cytokine assays; typhoid vaccination studies show sharp increases in the white cell count [49, 51, 52, 57, 60].

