**Data Analysis Plan** Each subject will have two visits (vaccine, placebo), and within each visit the primary outcomes (inflammation, behavioral responses) will be measured before injection and then serially (every 90 minutes) over the subsequent ~7.5 hours. Primary data analyses will use area under the curve (AUC) to summarize within-visit inflammatory and behavioral responses for each outcome. Hierarchical linear regression models (HLMs) will then be used to capture within-subject correlation across the two visits. If significant effects are found, secondary analyses will use more complex multi-level HLMs to model the individual time points within visit in order to identify at what time in the post-injection period effects arise.

For Hypothesis 1, baseline relationships between cardiorespiratory fitness and inflammation and behavioral outcomes will be evaluated using HLMs; subjects will have two baseline measurements, one before each injection, so an HLM is needed to control for the within-subject correlation. Outcomes in these models will be baseline (pre-injection) inflammation, depressive symptoms, cognitive problems, pain, and fatigue, and predictors will include cardiorespiratory fitness and visit (first or second). Tests of the main effect of cardiorespiratory fitness will investigate baseline relationships between these variables. The effect of vaccine on these outcomes over time will also be investigated using HLMs. AUC for each outcome at each visit will be the dependent variable, and predictors will include injection type (vaccine/placebo), cardiorespiratory fitness, and their interaction, as well as the baseline (pre-injection) outcome level. Separate models will be fit for each of the primary outcome AUCs (inflammation, behavioral responses) and the effect of interest will be the two-way interaction of cardiorespiratory fitness by injection type (which is a between-subject\*within-subject interaction). This term will allow us to investigate differences in response for the vaccine compared to placebo (injection type effect) and how these differences differ by fitness level (cardiorespiratory fitness by injection type interaction).

For Hypothesis 2a, baseline relationships between inflammation and age as well as the effect of age on vaccine responses will be investigated using HLMs similar to those described for Hypothesis 1 with age

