replacing cardiorespiratory fitness. For Hypothesis 2b similar HLMs will again be used, with depressive symptoms replacing cardiorespiratory fitness. For Hypothesis 2c, the HLMs with inflammation and behavioral AUC responses as outcomes will be modified by including both age and depression and their interaction as predictors. The test of the age by depression interaction will test whether the combination of older age and high depressive symptoms produces greater responses than the effect of either alone.

HLMs with AUC for inflammatory markers as well as behavioral responses as outcomes will also be used to test Hypothesis 3. Predictors will include injection type (vaccine/placebo), cardiorespiratory fitness, and age or depression, as well as all interactions and the baseline outcome level. Separate models will be used to test moderation of age and depression effects. To test whether cardiorespiratory fitness moderates the effect of age/depression on outcomes we will test the three-way interaction of injection type by age/depression by cardiorespiratory fitness. This is a three-way interaction, and we note that the primary interest is actually in the contrast testing the age/depression by cardiorespiratory fitness interaction for the vaccine injection. The post-placebo information serves to reduce error variance by allowing each woman to serve as her own control.

In all models we will control for BMI and insulin resistance to avoid possible confounding. Additionally, secondary analyses will control for use of aromatase inhibitors or tamoxifen; by including these variables as covariates, we will assess whether these medications impact cardiovascular (i.e., blood pressure, HRV) and inflammatory responses to the vaccine. Separately, we will assess whether tamoxifen or aromatase inhibitor use is related to cardiovascular variables and inflammation at baseline.

In secondary analyses, we will also assess antidepressant use as a possible confounder and control for this in analyses. We note again that the crossover design allows each woman to serve as her own control, thus mitigating the effect of possible confounders.

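### BMI and insulin resistance are to be controlled for, but the form of the terms is not stated; entered as main effects, they barely protect the H1 fitness-by-injection test

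*Combined protocol and SAP*

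**What the plan says.** Section G, Data Analysis Plan, defines the H1 response model on the area under the curve (AUC) at each visit: "predictors will include injection type (vaccine/placebo), cardiorespiratory fitness, and their interaction, as well as the baseline (pre-injection) outcome level". The effect of interest is the fitness-by-injection interaction. The covariate rule follows later in the same section: "In all models we will control for BMI and insulin resistance to avoid possible confounding". Section E says that HOMA-IR "will be used as a covariate in our analyses as an estimate of insulin resistance". No section says whether these covariates enter as main effects or also as products with injection type. The instruction to include all interactions belongs to the H3 model and covers injection type, fitness, and age or depression.

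For medication, Section B says "we will include aromatase inhibitor and tamoxifen use as covariates in secondary analyses". Section G adds that entering these variables as covariates will show whether they affect cardiovascular and inflammatory responses to the vaccine. It also says that the crossover lessens confounding because each woman is her own control.

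**The concern.** The fitness-by-injection term is the slope of the vaccine-minus-placebo difference on fitness. A covariate with one coefficient common to both visits has almost no part in that difference. What could distort the slope is a covariate that changes the size of the vaccine response and is related to fitness.

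The plan's own rationale points that way, within limits. HOMA-IR is included because "higher proinflammatory cytokine responses to stress occurred among individuals with greater insulin resistance", which describes a modified response rather than a constant shift, though to stress and not to a vaccine. On fitness, Section B says "Although central adiposity will be inversely associated with" VO2peak, though that is central adiposity and not BMI itself.

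At stake is a report that says BMI and insulin resistance were controlled when, for this test, they effectively were not. A medication main effect could likewise be read as a changed vaccine response.

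**Working it through.** **1. Algebra.** For one woman with fitness F and covariate C, let the outcome at a visit be a + (terms in F) + g·C, plus b·C at the vaccine visit only. In the difference D = vaccine − placebo, g·C cancels and b·C remains. A main effect fits g; only C × injection fits b. With C left out of the difference and corr(C, F) = r, the fitness slope picks up b·r per SD of fitness.

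The cancellation is exact with complete pairs and no covariate that varies by visit: in simulation, adding a BMI main effect changed the estimate by 0.000 in every run. With the visit-specific baseline outcome in the model, the mean change was at most about 0.004 mood points and the largest in any single run 0.16 (standard error about 0.36 to 0.39). Incomplete pairs and HOMA-IR measured at both visits were not simulated.

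**2. Size, closed form.** From the plan: N = 180, two-sided 5%. Assumed: residual SD of D, s = 1.0; effect b of 0.2 or 0.3 SD per SD; r from −0.1 to −0.5; no direct fitness effect. The noncentrality is b·|r|·√178 / √(s² + b²(1 − r²)), with 178 df.

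- b = 0.3, r = −0.2: 0.06 × 13.34 / √1.0864 = 0.77, rejection 12%.
- b = 0.3, r = −0.5: 0.15 × 13.34 / √1.0675 = 1.94, rejection 49%.

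| b | r = −0.1 | −0.2 | −0.3 | −0.4 | −0.5 |
|---|---|---|---|---|---|
| 0.2 | 6% | 8% | 12% | 18% | 26% |
| 0.3 | 7% | 12% | 21% | 34% | 49% |

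With s = 1.41 the whole grid runs from 5% to 28%.

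**3. Size, mixed model.** 2,000 simulated trials per setting, 180 women at two visits, random intercept, baseline outcome included, assumed BMI–HOMA-IR correlation 0.5. Rejection of fitness × injection:

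| r, b | No covariates | Main effects | Covariate × injection |
|---|---|---|---|
| −0.5, 0.3 | 46% | 46% | 5% |
| −0.2, 0.3 | 12% | 12% | 5% |
| −0.1, 0.2 | 6% | 5% | 5% |

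In the first row the mean estimates are −0.152, −0.152 and −0.004. A separate simulation on the mood scale, with an assumed 1.5 points per SD of BMI, gave 55%, 56% and 4% at r = −0.5, and 24%, 24% and 5% at r = −0.3.

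**4. Medication.** Let use shift both visits by m after baseline adjustment, and the vaccine visit by a further d. With roughly equal weight on the two visits, one common coefficient estimates m + d/2. So m = 0.2, d = 0 and m = 0, d = 0.4 both give 0.20; the drug × injection term gives 0 and 0.40.

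A shift already present before injection is largely absorbed by the baseline covariate. At baseline correlations of 0.8 or 0.9, a 0.2 SD shift leaves 0.2 × (1 − 0.8) = 0.04 or 0.2 × (1 − 0.9) = 0.02.

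**5. Power cost.** The plan's figure first. The hypothesized means give contrasts of 8.8 (three-way: (14.0 − 5.2) − 0), 5.4 (fitness × injection: 5.6 − 0.2) and 9.0 (depression × injection: 9.6 − 0.6). The residual SD is 7.7 × √(1 − 0.75²) = 5.09, with eight independent cells of 22.5 and 171 df.

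- Three-way: 8.8 / (5.09 × √(8/22.5)) = 2.90, power 82% (plan: 81%).
- Fitness × injection: 5.4 / (5.09 × √(4/45)) = 3.56, power 94%.

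If the added covariates explain a share R² of fitness, the t noncentrality is multiplied by √(1 − R²). For R² of 10%, 20% or 30% it becomes 3.37, 3.18 or 2.98, and power 92%, 89% or 84%. The loss is smaller if the pairing of visits is used.

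**The case against.** The strongest reply has four parts.

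- **The defect is inferred.** The plan never says main effects, and its H1 predictor list omits BMI and HOMA-IR altogether. This stands: the text shows an unstated form, not a wrong one. But if products were intended, they still have to be written down.
- **No size can be read from the documents.** Recruitment is designed "to maximize selection of more active women, particularly at higher BMIs", and women discordant on central adiposity and fitness are sought, which pushes the correlation down. At screening, "nurses will draw blood for assessment of anemia and hemoglobin A1C"; with diabetes excluded, this should narrow the range of HOMA-IR. The plan also promises to weigh effect size over significance. All of this stands, and it makes the 6% to 12% region more relevant than the 49% corner.
- **The fitness effect may run through the covariate.** If lower fitness raises BMI or insulin resistance, the unadjusted slope is a real total effect and the added term removes it. The documents do not settle this, so both estimates are needed.
- **The medication point is secondary, and baseline adjustment absorbs most of a persistent shift.** That is right about size. It does not let a coefficient that averages two visits answer a question about one of them.

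A reader might infer that the same defect is shown for age, depression or antidepressant use. The algebra carries over, but no text links age or depression to BMI or HOMA-IR, and Section B reports only small antidepressant effects on inflammatory markers. No change is asked there.

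**Conclusion.** The point holds as a gap in specification with a real consequence on the ordinary reading. As main effects, BMI and insulin resistance give the H1 fitness-by-injection test almost nothing beyond the crossover itself. The resulting distortion is about b·r per SD of fitness. In assumed settings this means rejection of about 6% to 12% at |r| of 0.1 to 0.2, and up to about 49% only at r = −0.5 with b = 0.3. It is nil if either link is zero.

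A reader might infer that the H1 fitness finding will be a false positive, or that the adjustment is useless throughout. The documents support neither. They give no fitness–BMI correlation and no BMI or HOMA-IR effect on the vaccine response, the covariate may be a mediator, and main effects are the right form for the baseline-association models.

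The medication statement fails on logic alone if use enters only as a main effect. The point is worth fixing before analysis; confidence is moderate.

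**What to change.** In Section G, Data Analysis Plan:

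- State the form in which each covariate enters each model.
- In the H1 AUC models, report fitness × injection with and without BMI × injection and HOMA-IR × injection. Say that the adjusted term excludes any fitness effect running through BMI or insulin resistance.
- In the secondary models that ask about the vaccine response, test tamoxifen and aromatase-inhibitor use × injection.
- Keep main-effect adjustment in the baseline models.
- Limit the statement that each woman is her own control to confounders that act equally at both visits.

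This changes wording only: height, weight, fasting glucose, fasting insulin and medication data are already planned. The costs are the power loss shown above (about 94% to 92%, 89% or 84% on the plan's independent-cell basis) and a narrower meaning for the adjusted term.

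As a separate correction, check the two-way power labels. The plan's means give about 94% for fitness × injection and above 99% for depression × injection (9.0 / 1.52 = 5.9), whereas the text prints them the other way round. This point does not depend on that.

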#### A.7.b Longitudinal Changes in Inflammation from Pre- to Post-Treatment in Cancer Survivors and Controls

We are currently completing a prospective study of inflammation, depression, and fatigue from pretreatment through survivorship in breast cancer survivors, as well as a benign comparison group (women who had a benign diagnosis following an initial abnormal mammogram). Baseline data on the stage 0-IIIA breast cancer survivors were collected before any cancer treatment including surgery, as well as 6 months and 18 months after completion of primary treatment (except tamoxifen/aromatase inhibitors). The average age in our sample is 55.39 (SD = 11.26, range = 26 to 88).

[figure not shown]

Figure 2: After adjusting for baseline levels, breast cancer survivors ( $N=124$ ) had significantly higher serum IL-6 (P-value for group effect=0.009), stimulated TNF- $\alpha$  (P-value for group effect=0.02), stimulated IL-6 (P-value for group effect=0.004), and stimulated IL-1 $\beta$  (P-value for group effect=0.008) after cancer treatment compared to control subjects ( $N=62$ ). Importantly, there were no differences in baseline cytokine levels for cancer subjects compared to controls after adjusting for age, BMI, depressive symptoms, and physical activity (all p-values  $>0.39$ ).

These data are important because they show the inflammatory changes that followed treatment for breast cancer compared to well-matched benign controls. Insofar as we know, these are the first prospective data to demonstrate post-treatment increases in inflammation compared to a non-treated group. These data are relevant to our proposed study because they highlight the fact that survivors already have heightened baseline

levels of inflammation before an immune challenge, and thus the potential moderating influences of cardiorespiratory fitness, age, and depression are even more consequential because of their greater vulnerability.

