## G. Statistical Methods

### Power and Sample Size

**NOTE: our projected sample for the two CRC admissions is 180, reflected in the sample size calculations below which are based on typhoid vaccine administration. The protocol describes a sample of 240 because any screening participants who are ineligible and/or who elect not to continue are counted in the total by the IRB.**

Power calculations were based on previously published data estimating the effect of typhoid vaccine on inflammation (IL-6) and mood. Wright [56] evaluated both proinflammatory cytokine responses and mood following injection of typhoid vaccine or placebo in 30 healthy male volunteers. The effect of vaccine on IL-6 was large; at 3h the mean IL-6 in the vaccine group was 1.59 (SD=0.81) compared to 0.53 (SD=0.30) in the placebo group, yielding an effect size of Cohen's  $d = 1.5$ . The effect of vaccine on negative mood was also large, though smaller than the effect on inflammation. At 3h post-injection the mean negative mood was 12.8 (SD=7.7) in the vaccine group compared to 7.4 (SD=5.8) in the placebo group, yielding an effect size of  $d = 0.76$ . Based on these results, we expect the effect of vaccine on mood to be smaller than the effect on IL-6, thus power calculations were designed to ensure adequate sample size to detect effects of vaccine on mood, which will ensure adequate power for IL-6 as well.

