The three specific aims for the proposed study are to evaluate (1) the effect of cardiorespiratory fitness on vaccine response, (2) the effect of age and depressive symptoms on vaccine response, and (3) the moderating effect of fitness on the age- and depression-related effects on vaccine response. Since each woman will serve as her own control by receiving both the vaccine and the placebo injection, the corresponding hypotheses all involve complex interactions: (1) the two-way interaction between fitness and injection type (vaccine/placebo), (2) the two-way interaction between age/depression and injection type, and (3) the three-way interaction of fitness by age/depression by injection type. Sample size requirements are considerably higher for testing higher-order interaction terms, thus we based required sample size on the tests of the third specific aim: the three-way interaction between fitness, age/depression, and injection type, while ensuring adequate power for the first two aims as well. Throughout we assumed 2-tailed tests with an 0.05 level of significance and used SAS PROC GLMPOWER for calculations.

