**Table: Hypothesized group means for negative mood for power calculations**

VACCINE RESPONSE (SD=7.7)			PLACEBO RESPONSE (SD=5.8)			
	Low Depression	High Depression		Low Depression	High Depression	
High Fitness	10	15.2	12.6	High Fitness	8.5	9.1
Low Fitness	11.2	25.2	18.2	Low Fitness	8.7	9.3
Average	10.6	20.2	15.4	Average	8.6	9.2

These means yield effect sizes for the vaccine response of  $d = 0.73$  for the average effect of fitness and  $d = 1.25$  for the average effect of depression. Importantly, in line with Hypothesis 3, they yield an effect size for depression of  $d = 1.8$  for women with low fitness and a smaller effect of  $d = 0.68$  for women with high fitness. Additionally, we will have baseline (pre-injection) measures of outcomes which will be used as covariates in models. In an ongoing study of breast cancer survivors, baseline negative mood was highly correlated with subsequent measures throughout the day, with  $r = 0.79-0.85$ . Inflammatory markers were similarly highly correlated, with correlations of  $r > 0.9$ . To be conservative in the power calculations we assume a single covariate with a correlation of  $r = 0.75$ . **Based on these hypothesized means and one covariate, a sample of size  $n = 180$  will give us 81% power to detect the three-way interaction effect of fitness by depression by injection type on mood. We will also have 94% power for the two-way interaction of depression by injection type and >99% power for the two-way interaction of fitness by injection type.** As previously noted, effects on IL-6 are expected to be larger and group differences should be as big or larger, thus this sample size should provide us the ability to detect the effects on IL-6 as well.

These calculations are conservative for several reasons. As previously noted, our sample is older than the sample on which we base our estimates, thus we will likely see even larger effects and more dramatic effects of age, depression, and fitness and should have higher power. Additionally, power calculations were made assuming fitness and depression were dichotomized; we will obtain continuous measurements of these covariates and thus expect higher power. We will also collect serial measurements of outcomes over time and thus expect to have higher power than if we only obtained a single post-injection measurement.

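### Chemotherapy regimen and time since treatment, both collected at screening and both plausible common causes of low fitness and high inflammation, are in none of the planned models

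*Combined protocol and SAP*

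**What the plan says.** Section G, Data Analysis Plan, names the terms of each model.

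- **Hypothesis 1, baseline models:** fitness and visit.
- **Hypothesis 1, AUC models:** injection type, fitness, their interaction and the pre-injection level of the outcome.
- **Hypothesis 3:** adds age or depression and all interactions.
- **Adjustment throughout:** "In all models we will control for BMI and insulin resistance to avoid possible confounding".
- **Secondary analyses only:** aromatase inhibitor or tamoxifen use, and antidepressant use.

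On treatment and fitness, Section B (Cardiorespiratory fitness) says that declines may come directly from chemotherapy's "toxic effects on pulmonary, cardiac, hematological, vascular, and skeletal muscle function, as well as deconditioning following treatment". On treatment and inflammation, the Overview says that cancer treatments can amplify it. Section A.7.b says of its survivor cohort that "these are the first prospective data to demonstrate post-treatment increases in inflammation compared to a non-treated group".

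On what is recorded, Section B (Online/phone screening) says: "To confirm eligibility, we will collect data on cancer stage, time since treatment, and treatment regimen". Eligible women had "either docetaxel/cyclophosphamide or doxorubicin/cyclophosphamide followed by paclitaxel to provide uniformity of prior treatment", and are recruited 1-8 years after primary treatment ended.

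**The concern.** Fitness is measured, not randomised. Treatment ended at least a year before the fitness test, so treatment history is a candidate common cause of fitness and inflammation and cannot be a consequence of the measured fitness. A woman with a harsher or more recent course could be both less fit and more inflamed. A model without that history would credit the difference to fitness.

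The trial's central claim is at stake. Section A.5 presents the study as a possible demonstration of how exercise produces its health benefits, and says that the vaccine model avoids problems of confounding. The plan's own practice also points towards adjustment: Section B would adjust for antidepressants if they were imbalanced, although it expects effects no larger than d = 0.17 on IL-6 and d = 0.29 on TNF-α.

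**Working it through.** **1. Which analyses are exposed.** In the vaccine-minus-placebo difference within a woman, anything that shifts both visits equally cancels. Anything that changes the size of the vaccine response does not. So:

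- The Hypothesis 1 baseline models are purely between women and have no crossover protection.
- Fitness by injection is biased only if treatment history alters the vaccine-minus-placebo response.
- For the same reason, adding treatment as a main effect alone would leave the interaction test essentially unchanged. Treatment by injection is needed.

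**2. False positives for fitness by injection.** The inputs from the documents are n = 180 (Power and Sample Size: "our projected sample for the two CRC admissions is 180") and two-sided 0.05 ("Throughout we assumed 2-tailed tests with an 0.05 level of significance and used SAS PROC GLMPOWER for calculations"). The documents give no correlations, so two are assumed: ρ between treatment history and fitness, and g between treatment history and the vaccine-minus-placebo difference. With no true fitness effect, the unadjusted standardised fitness coefficient is b = ρg and its standard error is √((1 − b²)/180). With δ = b/SE, the rejection rate is Φ(−1.96 + δ) + Φ(−1.96 − δ).

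Example at 0.3/0.3: b = 0.09, SE = √(0.9919/180) = 0.0742, δ = 1.21, rate = 22.8%.

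| ρ / g | b | Rate |
|---|---|---|
| 0.1 / 0.1 | 0.01 | 5.2% |
| 0.2 / 0.2 | 0.04 | 8.4% |
| 0.3 / 0.2 | 0.06 | 12.7% |
| 0.3 / 0.3 | 0.09 | 22.8% |
| 0.4 / 0.3 | 0.12 | 36.8% |

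A simulation of 4,000 trials per setting gave 8.5%, 23.1% and 35.8% at 0.2/0.2, 0.3/0.3 and 0.4/0.3, and 4.7-5.3% after adjustment. A second simulation, with 2,000 trials per setting and two visits per woman, gave 7%, 20% and 32%, and 4-6% with treatment by injection in the model. It scaled g to the residual SD, so g = 0.3 means a correlation of 0.3/√1.09 = 0.287, and its rates are a little lower. With g = 0 and ρ = 0.3 the unadjusted test rejected 5.3% of the time.

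**3. False positives in the baseline models.** The second simulation also let treatment shift the baseline level by 0.3 of the between-woman SD (assumed). For ρ from 0.2 to 0.4 the fitness test rejected about 10-24% of the time unadjusted and 4-6% adjusted.

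**4. Power cost, on the scale of the plan's own calculation.** The plan states 81% for the three-way term. From the table of hypothesised means:

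- Three-way contrast: [(25.2 − 11.2) − (15.2 − 10)] − [(9.3 − 8.7) − (9.1 − 8.5)] = 8.8.
- Residual SD with one covariate at r = 0.75: 7.7 × √(1 − 0.5625) = 5.09.
- With 180 observations over eight cells: SE = 5.09 × 8/√180 = 3.04, noncentrality 2.90, power 82.2%. With 176 observations (22 per cell) it is 81.3%. The stated figure is reproduced.
- Fitness by injection: contrast (18.2 − 12.6) − (9.0 − 8.8) = 5.4, SE = 5.09 × 4/√180 = 1.52, power 94%. The plan prints 94% for depression by injection and above 99% for fitness by injection. The table's means give the reverse, which is a separate matter.

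Regimen and years, each as a main effect and by injection type, use 4 degrees of freedom, which alone changes almost nothing. Overlap with fitness multiplies the contrast by √(1 − R²), with R² assumed:

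| R² | Fitness by injection | Three-way, if added to the primary test |
|---|---|---|
| 0 | 94% | 82% |
| 0.05 | 93% | 80% |
| 0.10 | 92% | 78% |
| 0.20 | 89% | 73% |

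**The case against.** The best defence is that the plan already controls much of this. Entry is limited to two regimens, stage I-IIIA and at least a year after treatment. Current heart disease, pulmonary disease and anemia are exclusions, which trims the extremes of the channels through which chemotherapy might lower fitness. The AUC models adjust for the baseline outcome, which Section G reports as correlating above 0.9 with later inflammatory markers, and each woman is her own control. Any effect of treatment on the level of inflammation is therefore largely absorbed there. BMI and insulin resistance may absorb more.

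Most of this stands for the AUC models. It does not cover the baseline models, and it leaves a two-level regimen difference and a seven-year spread in time since treatment.

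A reader might also infer that, on the plan's own account, treatment causes both low fitness and high inflammation, so that a fitness finding would be a treatment effect in disguise. The documents do not go that far. Their wording is *may* and *can*. Section A.7.b compares treated women with untreated benign controls, at 6 and 18 months after treatment, whereas every woman here was treated. Nothing in the documents shows that fitness or inflammation differs between the two regimens or across years 1-8, or that treatment history changes the response to the vaccine.

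**Conclusion.** The omission is real and worth correcting, but its size is unknown. The Hypothesis 1 baseline associations are plainly exposed. The fitness-by-injection test is exposed only if treatment history modifies the vaccine response. Every rate above rests on assumed correlations: at the low end there is no material problem, and the highest rate needs treatment history to explain 16% of the variance in fitness (0.4²) within a regimen-restricted sample. The documents do not support saying that the fitness result will be an artefact of treatment. They support saying that the planned models could not show whether it is, although the data to check will be in hand.

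**What to change.** In the Data Analysis Plan:

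- **Hypothesis 1, baseline models:** add regimen (two levels) and years since treatment as covariates.
- **Hypothesis 1, AUC models:** add each as a main effect and by injection type.
- **Reporting:** give the fitness estimate with and without these terms.
- **Hypothesis 3:** leave the primary three-way test unchanged. Add a sensitivity analysis with the same terms plus treatment by moderator and treatment by moderator by injection, where the moderator is age or depression. Without those further terms the three-way test is not adjusted for treatment history.

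This needs SAP wording and no new data. It uses two degrees of freedom in the baseline models and four in the AUC models, and loses some precision where treatment overlaps with fitness. Keeping the Hypothesis 3 terms out of the primary test avoids the fall below 80% shown in the last table at an R² of 0.10 or more.
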